7.2 Participant Withdrawal from the Study

All participants will be followed for survival until death, loss to follow-up, AstraZeneca closes the study, or withdrawal of consent, whichever occurs first.

- A participant may withdraw from the study at any time at his/her own request or may be withdrawn at any time at the discretion of the Investigator for safety, behavioural, compliance, or administrative reasons.
- A participant who considers withdrawing from the study must be informed by the Investigator about modified follow-up options (eg, telephone contact, a contact with a relative or treating physician, or information from medical records).
- At the time of withdrawal from the study, if possible, the 30-day Safety Follow-Up (SFU) visit should be conducted, as shown in the SoA. See the SoA for data to be collected at the time of study withdrawal and follow-up and for any further evaluations that need to be completed.
 - The participant will discontinue the study intervention and be withdrawn from the study at that time.
- If the participant withdraws consent for disclosure of future information, the Sponsor may retain and continue to use any data collected before such a withdrawal of consent.
- If a participant withdraws from the study, it should be confirmed if he/she still agrees for existing samples to be used in line with the original consent. If he/she requests withdrawal of consent for use of samples, destruction of any samples taken and not tested should be carried out in line with what was stated in the informed consent and local regulation. The Investigator must document the decision on use of existing samples in the site study records and inform the Global Study Team.

In addition, participants may be withdrawn from the study in the event that the Sponsor terminates this study (see Appendix [A 9](#)).

7.3 Procedures for Handling Participants Incorrectly Initiated on AZD4573 or Combination Therapy

Any participants determined to have met one or more of the exclusion criteria for study participation at study entry and continuing treatment with IP might constitute a safety risk.

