^a Changed from E to S as a minimum of 3 evaluable participants are needed to make a dose-escalation decision.

^b Changed from D to S as a minimum of 3 evaluable participants are needed to make a dose de-escalation decision.

Note: E = escalate to the next higher dose level, S = stay at the current dose level, D = de-escalate to the next lower dose level; DU = de-escalate to the previous lower dose and the current dose will never be used again due to unacceptable toxicity.

Abbreviations: D = de-escalation; DLT = dose-limiting toxicity; DU = dose unsafe; E = escalation; mTPI-2 = modified toxicity probability interval; S = stay.

A dose level will be considered as having unacceptable toxicity, with no additional participants enrolled at that dose level and above, if it has an estimated 95% or more probability of exceeding the 30% target DLT rate. Otherwise, dose escalation is terminated when the prespecified maximum target dose is reached (AZD4573 12 mg).

If a stay decision is made, additional participants may be enrolled (usually in cohorts of 2 to 6 participants) up to a maximum of 9 total evaluable participants for a given dose level and a maximum of 24 evaluable participants for dose setting (ie, a maximum of 9 evaluable participants at each of two dose levels and 6 evaluable participants at the third dose level).

At any timepoint during the study, the occurrence of a fatal AE deemed related to study therapy (after full etiological work-up and in discussion with the SRC) will result in accrual stoppage and a comprehensive review of safety. In addition, potential safety signals arising from Grade ≤ 4 treatment-related AEs will be reviewed in the context of the overall benefit/risk. On review any event deemed to adversely affect overall benefit risk will trigger an ad hoc SRC for comprehensive safety review.

In the case of PHL, if bilirubin remains elevated (compared to baseline) at 96 hours (-2/+12 hours) after the start of the infusion, the participant must be discontinued from the study and biochemistry followed until resolution. The Sponsor must be notified immediately.

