In general, if a participant experiences a Grade 1 or Grade 2 haematological or non-haematological toxicity, no dose modification is required. If a participant experiences a Grade 3 or Grade 4 toxicity, not attributable to the disease or disease-related processes under investigation, dosing might be interrupted and/or the dose reduced (see [Table 12](#) for acalabrutinib reduction options and [Table 13](#) for recommended dose modifications for AZD4573 and acalabrutinib) and supportive therapy administered as required. If the toxicity resolves or reverts to CTCAE Grade ≤ 2 within 21 days and the participant was showing clinical benefit, treatment with study treatment(s) may be restarted.

If the toxicity does not resolve to CTCAE Grade ≤ 2 within 21 days, then the participant should be withdrawn from the study and observed until resolution of the toxicity. Maximal drug interruption allowed for related toxicity for both AZD4573 and acalabrutinib is ≤ 21 consecutive days.

Table 13 Recommended Dose Modifications for AZD4573 and Acalabrutinib

Event ^a	Occurrence	Action with AZD4573	Action with Acalabrutinib
Tumour Lysis Syndrome (TLS) – Howard Modification of Cairo-Bishop Criteria			
Changes in uric acid, potassium, phosphorus, creatinine or calcium, or symptoms suggestive of clinically significant TLS, in the Investigator's judgement	Any	For any abnormal changes present before dosing, initiate supportive therapy and hold drug for up to 7 days. If not resolved, reduce by 1 dose level.	Withhold acalabrutinib until resolved, resume dosing at the same dose level upon resolution.
		For events of Grade 1 or 2 TLS, resume at same dose level upon resolution.	For events of Grade 1 or 2 TLS, resume at same dose level upon resolution.
		For 1st occurrence of Grade 3 TLS resume at the same dose upon resolution to Grade 1.	For 1st occurrence of Grade 3 TLS resume at the same dose upon resolution.

Table 13 Recommended Dose Modifications for AZD4573 and Acalabrutinib

Event ^a	Occurrence	Action with AZD4573	Action with Acalabrutinib

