Grade 3 thrombocytopenia without bleeding	Any	Withhold AZD4573 until Grade ≤ 2 or baseline level. Restart AZD4573 at the same dose level. Continued dosing can be considered at the discretion of the investigator after discussion with the medical monitor.	No action.
Grade 4 thrombocytopenia without bleeding requiring blood or platelet transfusion	1 st occurrence	Withhold AZD4573 until Grade ≤ 2 or baseline level. Restart AZD4573 at the same dose level.	Withhold acalabrutinib until Grade ≤ 2 or baseline level. Restart acalabrutinib at the same dose level.

Table 13 Recommended Dose Modifications for AZD4573 and Acalabrutinib

Event ^a	Occurrence	Action with AZD4573	Action with Acalabrutinib
	2 nd occurrence	Withhold AZD4573 until Grade \leq 2 or baseline level. Restart AZD4573 with 1 level dose reduction. If not recovered to Grade \leq 2 or baseline level discontinue.	Withhold acalabrutinib until Grade \leq 2 or baseline level. Restart acalabrutinib with 1 level dose reduction or discontinue (see Table 12).
	3 rd occurrence	Discontinue AZD4573.	Discontinue acalabrutinib.
Grade 3 or 4 thrombocytopenia with bleeding requiring blood or platelet transfusion	1 st occurrence	Withhold AZD4573 until Grade \leq 2 or baseline level. Restart AZD4573 with 1 level dose reduction. If not recovered to Grade \leq 2 or baseline level discontinue.	Withhold acalabrutinib until Grade \leq 2 or baseline level. Restart acalabrutinib with 1 level dose reduction or discontinue (see Table 12).
	2 nd occurrence	Discontinue AZD4573.	Discontinue acalabrutinib.

^a Adverse reactions are graded using National Cancer Institute CTCAE version 5.0. All grades refer to CTCAE grading except for TLS, which uses the Howard modification of Cairo-Bishop criteria ([Howard et al 2011](#)).

^b In cases where more than 21 days are needed, a decision to continue, modify, or discontinue study treatment will be made on a case-by-case basis in consultation with the principal Investigator and the Medical Monitor.

Abbreviations: ANC = absolute neutrophil count; ASCO = American Society of Clinical Oncology; CTCAE = Common Terminology Criteria for Adverse Events; ESMO = European Society for Medical Oncology; G-CSF = granulocyte-colony-stimulating factor; TLS = tumour lysis syndrome.

Dose modifications for AZD4573 and acalabrutinib for abnormal liver chemistry results are described in [Table 14](#).

Table 14 Recommended Dose Modifications for AZD4573 and Acalabrutinib for Abnormal Liver Chemistry Results

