Grade 4^c Isolated AST elevation $\geq 20 \times$ ULN without concomitant elevation in ALT $\geq 20 \times$ ULN or TBL $\geq 2 \times$ ULN	1st occurrence If recovered to Grade ≤ 1 or baseline level within 7 days of the start of the infusion allow rechallenge at same dose level 2nd occurrence If recovered to Grade ≤ 1 or baseline level within 7 days of the start of the infusion allow rechallenge with 1 dose level reduction 3rd occurrence Discontinue AZD4573	Withhold or continue acalabrutinib (at Investigator discretion, after discussion with the Medical Monitor). To prevent disease progression, monitor disease parameters closely. Monitor ALT, AST, ALP, and bilirubin at least 1x per week. After 7 days if hepatic enzymes appear to be improving and acalabrutinib was withheld, restart acalabrutinib at current dose level at the 1st occurrence and with 1 level dose reduction at the 2nd occurrence . Discontinue acalabrutinib at the 3rd occurrence .
Concurrent elevations in ALT, AST, or bilirubin (Please also refer to Appendix E for actions to be taken in the event of PHL)		
ALT or AST $\geq 3 \times$ ULN with TBL $\geq 2 \times$ ULN (Potential Hy's Law) AND INR $\geq 1.5 \times$ ULN (or $\geq 1.5 \times$ baseline if elevated at baseline) of any duration	Discontinue AZD4573.	Discontinue acalabrutinib.
ALT or AST $\geq 3 \times$ ULN with the appearance of fatigue, nausea, vomiting, right upper quadrant pain or tenderness, fever, rash, and/or eosinophilia $> 5\%$	Discontinue AZD4573.	Discontinue acalabrutinib.
ALT or AST $\geq 3 \times$ ULN and TBL $\geq 2 \times$ ULN where TBL does not return to baseline level within 96 hours (-2/+12 hours) from start of dose and/or AST or ALT do not return to baseline level within 7 days from start of dose	Discontinue AZD4573.	Discontinue acalabrutinib.

Event ^a	Action	
	AZD4573	Acalabrutinib
Grade 3 elevation ($\geq 5 \times$ ULN) in ALT or AST with TBL elevation above baseline level or ULN, but $< 2 \times$ ULN that do not return to baseline level within 7 days	Discontinue AZD4573.	Discontinue acalabrutinib.

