If bilirubin fails to resolve within 96 hours (-2/+12 hours) or transaminases fail to resolve within 7 days, or if the event is associated with significant clotting abnormality or clinical symptoms of liver disease, study treatment must be permanently discontinued (the participant remains on study for the 30-day SFU and long-term follow-up [LTFU] visits), and the event must be immediately communicated to AstraZeneca.

For guidance on treating liver toxicity, please refer to [Table 14](#) of this protocol.

During the course of the study the Investigator will remain vigilant for increases in liver biochemistry. The Investigator is responsible for determining whether a participant meets PHL criteria at any point during the study.

Please refer to [Appendix E](#) for the process to be followed to identify and appropriately report cases of PHL. It is not intended to be a comprehensive guide to the management of elevated liver biochemistries.

The Investigator will participate, together with the Medical Monitor, in review and assessment of PHL events to agree whether HL criteria are met. HL criteria are met if there is no alternative explanation for the elevations in liver biochemistry.

The Investigator is responsible for recording data pertaining to PHL/HL cases and for reporting AEs and SAEs according to the outcome of the review and assessment in line with standard safety reporting processes.

Regarding the hepatic toxicity events encountered to date with AZD4573, it has been observed that while the biochemical changes of increased transaminase with concomitant elevation in bilirubin seen in some participants could be classified as HL by its strict definition, they do not follow a pattern that is consistent with true HL predictive of hepatic injury, and are therefore 'PHL' cases. The events are rapidly resolved and to date have not led to any clinical sequelae or lasting hepatic injury. Repeated dosing with AZD4573 following these events has demonstrated that there is no consistent pattern of recurrence and no consistent increase in severity of the events if they do recur.

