Where contrast CT is contraindicated or unobtainable, MRI or CT (without contrast) with diagnostic quality (sufficient resolution to allow bi-dimensional measurements) may be used instead. In cases where MRI is desirable, the MRI must be obtained at baseline and at all subsequent response evaluations.

Following complete metabolic response, subsequent scheduled PET assessments are no longer mandatory. For participants with baseline hepatosplenomegaly, the cranial-caudal measurement of the spleen and longest diameter of the liver will be assessed at Screening and all subsequent response evaluations.

All response assessments will be made by the Investigator. All images for the assessment of response will be collected and stored for central review.

Participants should have radiographic tumour measurements done at the participating study centre or an acceptable alternate imaging facility using an identical imaging protocol and similar equipment. The same imaging equipment should be used for all scans whenever possible. The same radiologist should be assigned to read all the scans for a given participant throughout the study.

Participants who discontinue study intervention for reasons other than PD will continue to be scanned for disease response following the same schedule until documented PD, regardless of the start of new anti-lymphoma treatment.

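### Sections 15.2 and 15.12 take participants with unresolved toxicity out of the study where other sections stop only treatment, which exposes PFS and DoR to toxicity-related loss to follow-up

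*Protocol*

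**What the plan says.** Two passages of the Module 1 protocol remove a participant from the study because of toxicity:

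- Section 15.2, for potential Hy's Law with bilirubin still above baseline at 96 hours: "the participant must be discontinued from the study and biochemistry followed until resolution".
- Section 15.12, for toxicity that has not come down to Grade 2 or lower within 21 days: "then the participant should be withdrawn from the study and observed until resolution of the toxicity".

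Other passages meet the same triggers with a change of treatment only:

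- Section 17.1.10.9, when bilirubin has not resolved by 96 hours, stops study treatment permanently and adds that "the participant remains on study for the 30-day SFU and long-term follow-up [LTFU] visits".
- Table 14 (Section 15.12) has a row for raised transaminases and bilirubin "where TBL does not return to baseline level within 96 hours (-2/+12 hours) from start of dose". Its action is to discontinue AZD4573 and acalabrutinib; leaving the study is not mentioned.
- Table 13 (Section 15.12) discontinues the drug when a recurrent Grade 3 or 4 non-haematological toxicity has not resolved in 21 days. Under its footnote b, when more than 21 days are needed, "a decision to continue, modify, or discontinue study treatment will be made on a case-by-case basis".

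On follow-up after treatment stops, Section 17.4.2 says: "Participants who discontinue study intervention for reasons other than PD will continue to be scanned for disease response following the same schedule". Section 17.1.9.2 keeps participants who stop both drugs before progression in long-term follow-up. Section 7.2, the section on leaving the study, opens with: "All participants will be followed for survival until death, loss to follow-up, AstraZeneca closes the study, or withdrawal of consent, whichever occurs first". Sections 13.1 and 17.1.9.3 repeat that survival rule.

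**The concern.** Stopping treatment and leaving the study have different consequences for the data. A participant who stops treatment goes on to the 30-day safety visit, scans, progression follow-up and survival contacts. One who leaves the study under 15.2 or 15.12 is, by the words used there, followed only for biochemistry or until the toxicity resolves. A site that follows those two sections and a site that follows 17.1.10.9 would then produce different follow-up for the same event.

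If scans stop because of toxicity, the loss of PFS and DoR information is tied to an on-treatment outcome and cannot be assumed non-informative. The study is single-arm, so no comparison group would reveal the effect. PFS and DoR are secondary endpoints in Part B and exploratory in Part A (Table 7).

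**Working it through.** The plan states no figure on this point, so the check is a comparison of passages by trigger.

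| Trigger | Removes from the study | Concerns treatment only |
|---|---|---|
| Bilirubin unresolved at 96 h (-2/+12 h) | 15.2 | 17.1.10.9, which keeps the participant on study; Table 14 |
| Toxicity unresolved at 21 days | 15.12, text | 15.12, Table 13 and footnote b |

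**Are the two states really different in this protocol?** Yes. Section 7.1 governs discontinuation of study intervention and lists adverse events there. Section 7.2 governs withdrawal from the study and asks for the 30-day visit only where possible. The continued scanning in 17.4.2 and the long-term follow-up in 17.1.9.2 are written for participants who stop intervention or both drugs.

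**Which endpoints are exposed?** PFS and DoR depend on scans and progression follow-up, which the literal reading of 15.2 and 15.12 would end. OS depends on survival contacts. Sections 7.2, 13.1 and 17.1.9.3 end these only at death, loss to follow-up, study closure or withdrawal of consent; toxicity is not on the list.

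**Scale, cut-off rule.** Section 13.1 sets the data cut-off at 75% progressed or died, or 6 months' opportunity for follow-up, whichever is first. With the planned 21 or so per subtype, 0.75 × 21 = 15.75, so 16 events are needed. If k event-free participants leave with no further follow-up, at most 21 - k events can be seen. The event trigger is out of reach once 21 - k < 16, that is k ≥ 6; the 6-month trigger would still apply. The value of k is not given, and recruitment was stopped (Section 4.1), so 21 is a planning figure only.

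**Scale, OS illustration on assumed inputs.** The median of 6.41 months is the ibrutinib figure in Section 13.2.1. Assume exponential survival, and that 15% or 30% of those alive at month 2 leave then, with a doubled hazard and no further survival contact. These assumptions have no source in the protocol.

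- Monthly hazard h = ln 2 / 6.41 = 0.108
- Six-month survival without the added hazard: exp(-6h) = 0.523, which is also what Kaplan-Meier estimates if those leaving are censored
- Those leaving: exp(-2h - 4 × 2h) = exp(-10h) = 0.339
- True mixture at 15%: 0.85 × 0.523 + 0.15 × 0.339 = 0.495
- True mixture at 30%: 0.70 × 0.523 + 0.30 × 0.339 = 0.468
- Difference: 2.8 to 5.5 percentage points

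This shows what the mechanism could do if survival follow-up were dropped, which the protocol forbids. It does not estimate bias in this trial.

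**The case against.** The strongest reply is that the wording in 15.2 and 15.12 is merely loose. Section 16.1 sends the reader to 7.1, where adverse events lead to discontinuation of intervention, and Table 14 stops only the drugs. That reading is plausible, but it is not the only one: 15.2 uses mandatory language, and 7.1 and 7.2 keep the two states apart. The contradiction stands.

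Other parts of the reply succeed and limit the point:

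- A reader might infer that OS follow-up is lost and the survival curve inflated by 2.8 to 5.5 points. The documents do not support this. Survival follow-up is required for all participants, and 17.1.9.3 lets sites search public sources for vital status. Even on the assumed inputs, the difference is small beside the 95% half-width at n = 21, about 1.96 × √(0.25/21) = 21 points.
- A reader might infer that the route is common from the 4 transaminase or GGT dose-limiting toxicities in the monotherapy study (4 of 38, 10.5%). Those are not bilirubin failures at 96 hours. Section 13.3 describes AST elevations lasting under 4 days, and Sections 2.3.1 and 17.1.10.9 describe rapid resolution of the bilirubin events. No rate is given for the 21-day rule.
- A reader might infer that the curves must look too good. That needs toxicity to predict a worse outcome. Section 2.2.6 reports Grade 3 TLS in one participant with CR and one with SD, so the direction is open.
- A reader might infer that late SAEs are missed. Section 8.2.1 collects SAEs to 30 days after the last dose and requires suspected related ones to be reported afterwards.

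Recruitment has stopped and the database closes after the primary cut-off (Section 6.13), so few participants may be affected.

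**Conclusion.** The contradiction is real. It is sharpest for bilirubin unresolved at 96 hours, where 15.2 and 17.1.10.9 give opposite study status to the same event. At 21 days, the text of 15.12 conflicts with Table 13 and footnote b. The consequence is conditional: if a site follows 15.2 or 15.12 literally, scans and progression follow-up end because of toxicity, and PFS and DoR could be subject to toxicity-related loss to follow-up. OS is largely protected.

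No size or direction of bias can be given, because the protocol states no frequency for either route, and the censoring rules in Sections 18.4.5.3 to 18.4.5.5 were not in the text reviewed. No claim is made about the primary ORR endpoint. This is a correction worth making because it is cheap and protects secondary endpoints; it does not undermine the design.

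**What to change.** In 15.2 and 15.12, remove the words that take the participant out of the study. State instead that a participant whose study treatment is stopped for toxicity remains in the study for the 30-day safety visit, disease-progression follow-up and survival follow-up, in line with 17.1.10.9, 17.4.2 and 7.2.

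Two further conflicts are for the sponsor to reconcile; no treatment-stopping rule is proposed here:

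- The 21-day rule in the text of 15.12 against the case-by-case decision in Table 13 footnote b.
- The end of progression follow-up: 17.1.9.2 stops at progression or new anti-cancer therapy, under standard of care, while 17.4.2 continues scans on the same schedule to progression whatever new therapy is started.

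For anyone already withdrawn under the current wording who has not withdrawn consent, obtain vital status by the route in 17.1.9.3, in time for the survival calls planned for the week after data cut-off.

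The cost is two wording changes and a note to sites. Survival and standard-of-care progression follow-up are already in the Schedule of Activities. Its long-term follow-up column does not list protocol scans, so some alignment may be needed once 17.1.9.2 and 17.4.2 are reconciled.

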15.3 Definition of Dose-limiting Toxicity (DLT)

A Dose Limiting Toxicity is defined as any event that meets the DLT criteria listed in this section, unless unequivocally due to underlying malignancy or an extraneous cause.

Any participants receiving AZD4573 beyond the dose escalation/DLT-assessment period will be monitored for safety using the same DLT criteria used during the DLT-assessment period.

The SRC will make a recommendation to stop or continue recruitment after review of the data from each cohort (see Section [18.6](#)).

The DLT-assessment period applicable in Part A of this module is normally 5 weeks (DLT observation will continue throughout the study for Part A and Part B). Any participant who does not complete the DLT-assessment period in Part A may be replaced, with the exception of a participant who experiences a DLT; these participants will not be replaced.

Additional participants enrolled at a previously-cleared dose level to provide supplemental safety, efficacy, PK, and pharmacodynamics data will not be replaced or evaluated for DLT in support of dose-escalation decisions. However, these additional participants will be included in the determination of MTD/RP2D at the end of the dose-escalation process.

Any AE that meets the DLT criteria in the opinion of the principal Investigator should be reported to the Medical Monitor within 24 hours of knowledge of the event.

A DLT will be defined as the occurrence of any of the following, unless unequivocally due to underlying malignancy or an extraneous cause:

DLT criteria (CTCAE version 5.0):

- Any Grade ≥ 3 non-haematological toxicity except:
 - Grade 3 nausea, vomiting, or diarrhoea despite premedication that respond to medical management (eg, improve by 1 or more severity grade within 72 hours of onset of toxicity, or 96 hours [-2/+12 hours] from the start of dose, whichever is the sooner).
 - Grade ≥ 3 serum lipase and/or amylase that return to initial eligibility criteria within 72 hours of onset of toxicity or 96 hours (-2/+12 hours) post start of dose, whichever is the sooner. Grade ≥ 3 serum lipase and/or amylase that do not return to meet initial eligibility criteria within 72 hours of onset of toxicity or 96 hours (-2/+12 hours) post start of dose, whichever is the sooner, will be considered a DLT.

- A delay in dosing of more than approximately 7 consecutive days (\pm 2 days), in other words, more than 1 missed dose, due to a dose-related toxicity occurring during the 5-week DLT-assessment period (toxicity that is clearly and directly related to the primary disease or to another aetiology is excluded from this definition).

Isolated elevations of transaminases:

- Grade 3 elevations ($\geq 5 \times$ ULN) in ALT or AST, without concomitant elevation in total bilirubin $> 2 \times$ ULN, that do not return to Grade 1 within 7 days from start of dosing.
- Grade 4 elevations in ALT ($\geq 20 \times$ ULN) of any duration irrespective of total bilirubin.
- Grade 4 elevations in AST ($\geq 20 \times$ ULN) without concomitant elevation in ALT $\geq 20 \times$ ULN or total bilirubin $\geq 2 \times$ ULN that do not return to Grade 1 within 7 days from start of dosing.

Elevations in transaminases with concomitant elevation of bilirubin (Potential Hy's Law [PHL]):

- Elevations in ALT or AST $\geq 3 \times$ ULN with concomitant elevation in total bilirubin $\geq 2 \times$ ULN where bilirubin does not return to meet initial eligibility criteria within 72 hours of onset or 96 hours of start of dosing (-2/+12 hours) whichever is the sooner, and/or ALT or AST do not return to meet initial eligibility criteria within 7 days post start of dose.
- Elevations in ALT or AST $\geq 3 \times$ ULN with concomitant elevation in total bilirubin $\geq 2 \times$ ULN and INR $> 1.5 \times$ ULN (or $> 1.5 \times$ baseline, if elevated at baseline) of any duration.
- Elevations in ALT or AST $\geq 3 \times$ ULN with concomitant elevation in total bilirubin $\geq 2 \times$ ULN of any duration if associated with symptoms or signs of liver impairment (eg, appearance of fatigue, nausea, vomiting, right upper quadrant pain or tenderness, fever, rash, and/or eosinophilia $> 5\%$).

Any of the following haematological toxicities:

- CTCAE Grade 4 neutrophil count decrease lasting > 7 days, despite growth factor support.
- Grade ≥ 3 febrile neutropenia (absolute neutrophil count [ANC] $< 1.0 \times 10^9/L$, fever $> 100.9^{\circ}\text{F}$ [or $> 38.3^{\circ}\text{C}$]) of any duration despite supportive care.
- CTCAE Grade 4 thrombocytopenia lasting more than 7 days or Grade ≥ 3 thrombocytopenia, of any duration, associated with \geq Grade 2 bleeding.

- CTCAE Grade 4 anaemia despite transfusion.

Any Tumour Lysis Syndrome meeting the following criteria:

- Grade ≥ 3 clinical TLS ([Appendix F](#)) that occurs despite protocol-recommended management will be considered a DLT.
- Laboratory TLS ([Appendix F](#)) will be considered a DLT if the metabolic abnormalities do not resolve within 5 days despite protocol-recommended management.

Note: All DLT events of TLS should be graded according to the Howard modification of the Cairo-Bishop criteria as part of TLS monitoring (Section [17.1.5](#) and [Appendix F](#)), while CTCAE grade should be applied on AE/SAE reports.

The definition of DLT excludes:

- 1 Grade 3 fatigue for ≤ 7 days after onset.
- 2 Isolated laboratory changes of any grade without clinical sequelae or clinical significance, with the exception of transaminase and bilirubin abnormalities described above.
- 3 Isolated changes in GGT (ie, with no corresponding elevation in AST, ALT, ALP, Total bilirubin or INR, and no symptoms suggestive of hepatic injury) will not be classified as a DLT.

